CLINICAL STUDY PROTOCOL

PROTOCOL TITLE

**A DOUBLE BLIND, RANDOMIZED, PLACEBO CONTROLLED STUDY
TO EVALUATE EFFICACY AND SAFETY OF “VIRACIDE”
IN THE MANAGEMENT OF CORONA VIRUS DISEASE 2019 (COVID-19)**

**Protocol Number: NS-VC-CT01-20
Clinicaltrial.gov ID: NCT04596085**

STUDY SYNOPSIS

Title	A double blind, randomized, placebo controlled study to evaluate efficacy and safety of “ViraCide” in the management of corona virus disease 2019 (COVID-19).
Study Description	
This is a double blind randomized placebo controlled study will be conducted on 124 subjects, 50 years and older with mild or asymptomatic COVID-19. If symptomatic, symptoms are mild (cough, weakness, sore throat, low grade fever 38.50C, respiratory rate should not be more than 22 / min, resting SpO2 >95%, normal highly sensitive C-reactive protein (HS-CRP) (<10mg/L). There are no signs of dehydration, sepsis or shortness of breath.
 
The study will be conducted at two centers. There will be a screening visit at Day -4 followed by three visits at the center at Days 1, 7 and 15 and a follow-up visit on Day 28. All participants will be randomized to receive either ViraCide (investigational product) or matching placebo. All subjects will receive SOC therapy.
 
Note: If subject is discharged before Day 15 PI’s discretion as per patients health condition, then assessments scheduled for Day 15 will be carried out on the discharge day (as far as possible and those not performed will be noted on appropriate CRF page) and Day 15 visit will be done telephonically.

Investigational Product/Study drug	ViraCide softgels given per orally
Comparison product	Matching placebo of ViraCide softgels given per orally
Study Design	Double blind, randomized, placebo controlled study. Subjects will be randomized to the experimental and control groups in a 1:1 ratio. In each group 62 subjects will be recruited, a total of 124 subjects. Subjects of the experimental arm will receive treatment with Study Drug, ViraCide and SOC. The control group will receive matching placebo and SOC. The study consists of the stages of screening, therapy, observation. There will be no switching of subjects between the arms. Participants will receive Study drug or matching placebo for 14 days during the study.
Sample Size	124, including 10% dropouts

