Stopping the Study Drug	
 1. Completing 14 days of treatment 2. Progression to severe COVID-19: ViraCide will be stopped if subjects progresses to severe COVID-19 and require ICU admission, mechanical ventilation and any such situation where according to the PI the subject

	
cannot continue ViraCide. However, subject will be followed-up to capture data on ICU admission, incidence and mortality
 
 3. Progression of comorbid condition requiring admission to ICU or inability of the subject to take anything orally. However, subject will be followed-up to capture data on ICU admission, incidence and mortality 4. Subject's participation to the study is terminated 5. Study is terminated
Termination of Subject's Participation in the Study	
Any participant can be removed from the study:
 
 1. By his/her own free will to not continue in the study. Subject withdrawal of informed consent. 2. Loss of contact with the subject during the study. 3. Does not comply with dosing schedule (75%-125% non-compliance) 4. The development of AE / SAE requiring the withdrawal of the study drug. However all AE / SAE will be followed-up till the study duration 5. Pregnancy confirmed anytime during the study duration 6. Another reason, which, according to the PI, requires the termination of the subject's participation in the study.
Study Termination	
The study can be terminated if
 
 1. There is a major deviation in Protocol 2. Another reason, which, according to the PI, requires study termination

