STATISTICAL ANALYSIS PLAN

STUDY TITLE:

A DOUBLE BLIND, RANDOMIZED, PLACEBO CONTROLLED

STUDY TO EVALUATE EFFICACY AND SAFETY OF

“VIRACIDE”

IN THE MANAGEMENT OF

CORONA VIRUS DISEASE 2019 (COVID-19)

Version No. – 01

Dated: 04th June 2020

Protocol ID – NS-VC-CT01-20

Clinicaltrial.gov ID: NCT04596085

Confidential & Proprietary

the unauthorized use, disclosure, distribution or copying of these information is strictly prohibited

Confidential

Page

1 of 11

Table of Contents

[1 Definitions](#)

[2 Objectives](#)

[3 Analysis Sets](#)

[4 Data handling](#)

[5 Statistical methods](#)

[5.1 Descriptive methods](#)

[5.2 Primary analysis](#)

[5.3 Analysis of the secondary endpoints](#)

[5.4 Safety and/or further analyses](#)

[6 Listings, tables, figures](#)

[7 Graphs](#)

[8 Software](#)

Confidential & Proprietary

the unauthorized use, disclosure, distribution or copying of these information is strictly prohibited

Confidential

Page

2 of 11

1 Definitions

The following abbreviations will be used in this statistical analysis plan.

ITT	Intention-to-treat
PP	Per protocol
IP	Investigational product
AE	Adverse Event
SAE	Serious adverse event
TTCI	Time to clinical Improvement
SPO2	Oxygen saturation
ICU	Incentive Care Unit

Confidential & Proprietary

the unauthorized use, disclosure, distribution or copying of these information is strictly prohibitea

2 Objectives

Primary Efficacy Endpoint:

1. TICI using NEWS Score [Time Frame: First treatment date up to when PCR is negative]

The median time in days from the start of treatment with the study drug / placebo to the persistent achievement of all of the following criteria:

- Stopping a fever (which is defined as a decrease in axillary temperature below 37 ° C without the use of antipyretic drugs);
- Respiratory rate <22 / min;
- Oxygen saturation (SPO2) > 95% when breathing in atmospheric air. Measured using pulse oximetry
- Systolic blood pressure ≤200 mmHg
- Pulse rate 51-90 beats/minute
- Is conscious and alert

[Note: Persistent achievement means the preservation of each of the criteria for at least 7 days.]

2. TTIC using 7-point ordinal scale
3. Rate of progression to severe/critical COVID-19 disease based on NEWS score [Time frame: First treatment date up to 28 days]
4. Rate of progression to severe/critical COVID-19 disease based on 7-point ordinal scale [Time frame: First treatment date up to 28 days]

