5. Time to COVID-19 nucleic acid testing negativity in oropharyngeal/nasal swab) [Time Frame: First treatment date up to 28 days]

Confidential & Proprietary

The unauthorized use, disclosure, distribution or copying of these information is strictly prohibited

Secondary Efficacy Endpoints:

1. Incidence of ICU admissions [Time Frame: 28 days]
2. Subject survival rate [Time Frame: 28 days]
3. Incidence of mechanical ventilation [Time Frame: First treatment date up to 28 days]
4. Time to COVID-19 nucleic acid testing negativity in oropharyngeal/nasal swab) [Time Frame: Days 1, 7, 15]
5. Change in clinical or laboratory assessment of comorbid condition [Time Frame: First treatment date up to 28 days]
6. Percent of participants with worsening comorbid condition [Time Frame: First treatment date up to 28 days]

Safety Endpoints

1. Proportion of subjects in the treatment arm who had AE, SAE
2. Proportion of subjects in the placebo arm who had AE, SAE

Confidential & Proprietary

Any unauthorized use, disclosure, distribution or copying of these information is strictly prohibited

3 Analysis sets

Per protocol subset (PP)

Subjects without any Major protocol violation would be included in the per-protocol population, including those subjects who have completed all the visits, who did not take any prohibited medications during the study period and whose CRF was completed as requested.

Modified Intention to treat subset (mITT)

The term “mITT” includes all randomized subjects who met all inclusion/exclusion criteria, administered at least one dose of assigned product with at least completed one visit will be included in the mITT population.

Safety analysis subset

The safety population will consist of all subjects enrolled in the study, who have received at least one dose of study products i.e. mITT population.

Methods of Analysis

Primary Efficacy and secondary endpoints will be analyzed using the PP & mITT population. And Safety variables as per mITT only.

4 Data Handling

Data entry into CRF must be performed as per general CRF data entry guidelines, summarized at the time of data entry feasibility training. Data entry will be made as per source document without interpretation or modification to maintain consistency and accuracy of the data. Study specific

Confidential & Proprietary

Any unauthorized use, disclosure, distribution or copying of these information is strictly prohibited

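### The per-protocol set drops subjects who die before the last required visit, yet 28-day survival and other severe outcomes are to be analysed in it

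*SAP*

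**What the plan says.** SAP section 3 (Analysis sets) starts the PP definition from the absence of a major protocol violation and continues: "including those subjects who have completed all the visits, who did not take any prohibited medications during the study period". It adds that the CRF must be complete. Under Methods of Analysis in the same section: "Primary Efficacy and secondary endpoints will be analyzed using the PP & mITT population". No endpoint is exempted, neither set is named as the lead, and nothing says that a recorded death counts as completing the visits.

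The endpoints covered (SAP section 2) include, as secondary, "Subject survival rate [Time Frame: 28 days", "Incidence of ICU admissions [Time Frame: 28 days" and "Incidence of mechanical ventilation [Time Frame: First treatment date up to 28 days", and, as primary, progression on the NEWS score and "Rate of progression to severe/critical COVID-19 disease based on 7-point ordinal scale [Time frame: First treatment date up to 28 days". That is five of the 11 listed efficacy endpoints, two of them primary.

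On what a visit is, the protocol points two ways. The Study Description schedules "three visits at the center at Days 1, 7 and 15 and a follow-up visit on Day 28". The Visits of Assessment row lists Day 28 too, but its opening line counts screening and three visits and mentions a telephone follow-up separately. The same row lets a Day 15 visit take place by telephone after early discharge. The SAP does not define the term.

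For subjects who stop the study drug because of severe disease, the protocol provides that the "subject will be followed-up to capture data on ICU admission, incidence and mortality".

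**The concern.** Membership of the PP set depends partly on the outcome it is used to measure. A subject who has died cannot complete a later visit, so an all-visits rule removes deaths from the numerator and the denominator of the survival rate together. The arm with more deaths loses more of them, and the PP comparison moves towards no difference. The same happens to the fatal cases among subjects admitted to ICU, ventilated or progressing.

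A PP table showing equal survival could then be read as a planned efficacy or safety reassurance while carrying little or no information on mortality. Because the SAP names no lead set and no rule for when PP and mITT disagree, the choice of which result to stress could be made after the results are known.

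**Working it through.** **The plan's own figure.** Neither document gives a PP set size, a mortality or a progression rate. The only related figure is the sample size in the protocol's Statistical Analysis row: 112 completers plus 10% gives 112 × 1.10 = 123.2, rounded up to 124, or 62 per arm (56 × 1.10 = 61.6). This reproduces. The examples below use 62 per arm, assume that all 62 are in mITT, and ignore other reasons for leaving PP. All event counts and rates are assumptions.

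**Survival if Day 28 is a visit.** With n subjects and d deaths before Day 28 in an arm:

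- mITT survival = (n − d)/n
- PP survival = (n − d)/(n − d) = 100% for any d < n

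With 1 death on ViraCide and 4 on placebo, mITT survival is 61/62 = 98.4% vs 58/62 = 93.5%, and PP survival is 61/61 vs 58/58, both 100%. The 100% needs no assumed rate; it follows from the definition.

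**Survival if only the centre visits to Day 15 count.** Let q be 28-day mortality and f the share of deaths before Day 15. Then PP survival = (1 − q)/(1 − q × f).

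| q | True survival | f = 0 | f = 0.5 | f = 1 |
|---|---|---|---|---|
| 5% | 95.0% | 95.0% | 0.95/0.975 = 97.4% | 100% |
| 10% | 90.0% | 90.0% | 0.90/0.95 = 94.7% | 100% |

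**ICU admission, fatal cases only.** Let r be ICU incidence and k the share of ICU patients who die before the last required visit, with no deaths outside ICU. PP incidence = r(1 − k)/(1 − r × k). With r = 10% and k = 40%, this is 0.06/0.96 = 6.25% instead of 10%. The rate is biased downwards but not forced to zero.

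**Progression, over a range of missed visits.** Assume 6 progressors on placebo and 2 on ViraCide. The mITT rates are 6/62 = 9.7% vs 2/62 = 3.2%, a difference of 6.5 points. Each progressor who misses a visit leaves both numerator and denominator.

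| Progressors missing a visit (placebo, ViraCide) | PP placebo | PP ViraCide | Difference |
|---|---|---|---|
| 0, 0 | 6/62 = 9.7% | 2/62 = 3.2% | 6.5 points |
| 3, 1 (half in each arm) | 3/59 = 5.1% | 1/61 = 1.6% | 3.4 points |
| 4, 1 | 2/58 = 3.4% | 1/61 = 1.6% | 1.8 points |

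An equal proportion missing in each arm is already enough to shrink the difference; uneven loss shrinks it further in this example.

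**The case against.** The strongest reply is that the trial already has a sound analysis of these endpoints. The mITT set keeps every eligible subject with one dose and one completed visit, so deaths after that point are counted. This stands, and it limits the seriousness of the point. It does not make the PP survival table informative, and the SAP does not label PP as supportive.

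The wording can also be defended. The lead criterion is freedom from a major violation, death is not called a violation, and the all-visits clause is introduced loosely. But unless that clause restricts membership it does nothing, so the restrictive reading is the natural one.

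Three stronger readings are tempting, and the documents do not support them:

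- A reader might infer that PP survival must be 100% on any reading. That depends on the Day 28 contact being a visit. The Study Description supports it, but the count in the Visits of Assessment row leaves room for the narrower reading, on which deaths after Day 15 can stay in (unless the CRF clause removes them).
- A reader might infer that subjects who go to ICU, are ventilated or progress all leave PP. Nothing says that they miss visits. Subjects are managed in isolation wards and are followed after stopping the drug, so survivors can complete their visits. Only the fatal cases are clearly lost; further loss is plausible but inferred.
- A reader might infer that the follow-up collected after progression is shut out of the PP analyses altogether. It is not: progressors who complete their visits remain in PP with their data.

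**Conclusion.** The point holds in a limited form. As written, the SAP produces a PP survival result selected on survival: 100% in both arms if Day 28 is a visit, and overstated whenever deaths occur before Day 15 if it is not. ICU admission, ventilation and both progression endpoints are understated in PP by at least the deaths before the last required visit. How far the comparison between arms is distorted cannot be determined from the documents; in the assumed progression example the PP difference lies anywhere from 6.5 points (no loss) to 1.8 points.

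The conclusion rests on reading the all-visits clause as a condition of membership and on the absence of any exception for death. Since mITT is planned for the same endpoints, this should be fixed, but it does not undermine the trial's ability to compare survival.

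**What to change.** Two statements in SAP section 3, settled before unblinding:

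1. Survival, ICU admission, mechanical ventilation and both progression endpoints are analysed in mITT only.
2. For the endpoints that keep a PP analysis, visits or CRF pages missing because of death or another outcome event (ICU admission, ventilation, progression to severe disease) do not exclude a subject from PP.

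The first statement alone cures the survival problem, whichever way the Day 28 contact is classified. The second protects the remaining PP endpoints, such as time to clinical improvement, from the same selection, and covers the CRF clause as well as the visit clause.

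No new data are needed and no clinical rule changes. The cost is that the PP set becomes slightly less complete, and the five endpoints no longer have a PP table.

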	
 7. Subjects having history of organ failure or conditions requiring ICU monitoring and treatment, such as severe liver disease, severe renal dysfunction, upper gastrointestinal hemorrhage, disseminated intravascular coagulation or any other condition that in the PI's opinion makes the subject unfit to participate 8. Respiratory failure, ARDS or need of mechanical ventilation 9. History of acute exacerbation of comorbidity like heart failure, diabetic ketoacidosis, myocardial infection, major cardiac rhythm disorder or any other condition that in the PI's opinion makes the subject unfit to participate 10. History of or current hepatic failure or severely compromised liver function, or renal failure or having chronic kidney disease or acute renal failure 11. History of or currently receiving treatment for an endocrine disorder like hypothyroidism, hyperthyroidism that is likely to affect the basal heart rate. 12. History of or currently under treatment for asthma [exception: patients with history of asthma, not on medications/inhalers/nebulizers for at least 6 months
	
before study start), COPD, bronchiectasis, asbestosis and other such chronic lung conditions that can compromise SpO₂ and RR.
 
 13. HIV, HBsAg, HCV positive 14. Any condition causing immunodeficiency 15. Systemic connective tissue disease or any autoimmune disease that is likely to affect HS-CRP levels 16. History of epilepsy/epileptic fit/convulsions in last 6 months or currently on treatment for it 17. History of or currently having malignancy and being treated for it. (exception: histologically confirmed and cured carcinoma in situ) 18. Hypersensitivity reaction to Study drug/placebo 19. Any psychiatric issue for which the subject is currently undergoing treatment 20. Any history of drug/alcohol dependence within 30 days of screening or current drug/alcohol dependence 21. Inability to understand the requirements of the Research Protocol and follow the research procedures. 22. Pregnant or lactating; 23. Not willing to use adequate contraception during study duration 24. Participation in any other clinical study less than 3 months before the start of the study.

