Visits of Assessment	
Screening and 3 visits and one telephonic follow-up
 
Screening Inclusion/Exclusion Criteria, Subject Inform Consent, Demography, Medical History, Physical Examination, Vital Signs, HIV; HBsAg; HCV; Hs-CRP; Pulse oximetry; NEWS scoring; 7- point ordinal scoring; Medication list review (medications being taken for comorbid conditions), Lab assessment; Urine analysis Note: Patients who do not meet the study inclusion exclusion criteria during screening should not be randomized into the study.
 
Day 1 Randomization, Vital Signs, Pulse oximetry, AE/SAE, Concomitant Medication, ViraCide/ Placebo treatment start, NEWS scoring; 7-point ordinal scoring
 
Day 7 Physical Examination, Vital Signs, AE/SAE, Concomitant Medication, ViraCide/ Placebo Compliance check, Pulse oximetry; NEWS scoring; 7-point ordinal scoring. (Note: If the subject is discharged on this day as per PI's discretion and patient's health condition then assessment scheduled for day 15 will be carried out on discharge day).
 
Day 15 Physical Examination, Vital Signs, AE/SAE, Concomitant Medication, ViraCide/ Placebo treatment end, RT-PCR for

	
Sars- Co-V2, Hs-CRP, Safety Lab Tests, Pulse oximetry; NEWS scoring; 7-point ordinal scoring, ViraCide/ Placebo Compliance check, Lab assessment including urine analysis
 
Day 28 Phone call follow up for time :
 
 • until negative RT-PCR for Sars-Co- V2, COVID-19 related mortality, • development of any COVID-19 symptom, • development of any worsening of comorbid condition; • Development of new AE/SAE; Resolution status of previous AE/SAEs 
Note: If subject is discharged before Day 15 on PI's discretion as per patients health condition, then assessments scheduled for Day 15 will be carried out on the discharge day (as far as possible and those not performed will be noted on appropriate CRF page) and Day 15 visit will be done telephonically.

Laboratory Investigations	
Screening: Recording RT-PCR- Sars-Co-V2 result; Urine pregnancy test; HIV; HBsAg; HCV; Hs-CRP; Hematology* + Biochemistry + Urine analysis*; ECG
 
Day 1: No labs
 
Day 7: No labs
 
Day 15: Oropharyngeal/nasal swab for PCR- Sars-Co-V2; Hematology* + Biochemistry + Urine analysis*; ECG; Serological biomarker: Hs-CRP

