5.4 Safety Analysis

Incidence and rate of adverse events.

AEs and SEs will be summaries counting both the number of separate events and the number of subjects experiencing events occurring during the study period will be provided overall, per system organ class and preferred term by presenting.

Confidential & Proprietary

the unauthorized use, disclosure, distribution or copying of these information is strictly prohibitea

Furthermore, similar summaries will be provided stratified according to the seriousness, severity, and relationship to the study medication. The percentage of cases with an event will be analyzed and compared by the Chi-Square test. Mean changes in in vital signs and Laboratory variables, will be assessed by using student t-test for with in groups and analysis of variance for comparison between groups.

6. Listing of Tables

- Participant Disposition
- Demographical and baseline characteristics with comparison of demographical and baseline characteristics
- Profile of Medical History and clinical Examinations
- Changes in Vital Signs
- Comparison of Mean Time to Clinical Improvement (TTCI) using NEWS Score
- Comparison of Mean Time to Clinical Improvement (TTCI) using 7 point ordinal scale.
- Rate of progression to severe/critical COVID-19 disease based on NEWS score [Time frame: First treatment date up to 28 days
- Rate of progression to severe/critical COVID-19 disease based on 7point Ordinal scale [Time frame : First treatment date up to 28 days

Confidential & Proprietary

The unauthorized use, disclosure, distribution or copying of these information is strictly prohibited

- Mean Time to COVID-19 nucleic acid testing negativity in oropharyngeal/nasal swab) [Time Frame: First treatment date up to 28 days]
- Incidence of ICU
- Profile of subject survival rate
- Incidence of Mechanical ventilators
- Time to COVID-19 nucleic acid testing negativity in oropharyngeal/nasal swab) [Time Frame: Days 1, 7, 15]
- Percent of participants with worsening comorbid condition [Time Frame: First treatment date up to 28 days]
- Changes in clinical assessment of co morbid conditions
- Comparison of Changes Laboratory Variables
- Profile of adverse events in each group
- Profile of Serious adverse events in each group

7. Graphs

Individual Graphs for all Primary and secondary variables

8. Software

SPSS Version 10.0

Confidential & Proprietary

The unauthorized use, disclosure, distribution or copying of these information is strictly prohibited

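### The SAP equates the safety set (at least one dose) with the narrower mITT set and runs safety on mITT only, so a dosed subject can be left out of the AE/SAE tables

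*SAP*

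**What the plan says.** Three statements in SAP section 3 bear on this point.

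- **Safety set.** All enrolled subjects "who have received at least one dose of study products i.e. mITT population".
- **mITT set.** It consists of "all randomized subjects who met all inclusion/exclusion criteria, administered at least one dose of assigned product with at least completed one visit".
- **Set used for safety.** After assigning the efficacy endpoints to the PP and mITT sets, the Methods of Analysis paragraph adds: "And Safety variables as per mITT only".

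SAP section 5.4 specifies the AE and SAE summaries and the between-arm comparison ("The percentage of cases with an event will be analyzed and compared by the Chi-Square test") without naming a population. SAP section 5.1 uses the label Safety population once, for medical history and physical examination, and does not redefine it. The protocol synopsis defines no analysis sets.

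On data collection, the protocol's Visits of Assessment schedules AE/SAE recording on Days 1, 7 and 15 and asks about new and ongoing events at the Day 28 call. It makes no exception by eligibility status. On eligibility, the screening note there says: "Patients who do not meet the study inclusion exclusion criteria during screening should not be randomized into the study".

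**The concern.** A safety set is meant to hold everyone exposed to the product, whether or not they should have been enrolled. The safety sentence begins with that rule and ends by replacing it with a set that has extra entry conditions. The Methods of Analysis line then points to the narrower set. Two programmers following the SAP could build different denominators, and the one who follows the final instruction would drop exposed subjects.

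Safety is the protocol's secondary objective, and the proportions with an AE or SAE are named endpoints in both documents. With 62 subjects per arm, serious events may be few, so the classification of one subject can show in the table. An event in an excluded subject would have been collected under the visit schedule and then left out of the planned summaries.

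**Working it through.** The plan gives no count of dosed subjects outside mITT and no expected AE rate, so there is no stated figure to reproduce. The check is a comparison of the definitions, followed by an illustration of size.

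**Step 1. Compare the conditions (SAP section 3).**

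| Condition | Safety set, as first described | mITT |
|---|---|---|
| At least one dose | yes, of either study product | yes, of the assigned product |
| Every eligibility criterion met | not required | required |
| At least one visit completed | not required | required |

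Every mITT subject has been dosed, but not every dosed subject need be in mITT. The sets coincide only if all dosed subjects are eligible, receive the assigned product and complete a visit.

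**Step 2. Who can fall between the two sets.**

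- *Eligibility breach found after dosing.* The synopsis lists 10 inclusion and 24 exclusion criteria. Some rest on history that may come to light later, for example exclusion 24, "Participation in any other clinical study less than 3 months before the start of the study". The screening note limits this group but does not cover breaches discovered afterwards.
- *Only the other arm's product received.* This needs every dose to be wrong. It is possible, but nothing in the documents suggests that it is likely.
- *No completed visit.* The SAP does not say which visit counts. Randomization and start of treatment both take place on Day 1, so if Day 1 counts, the condition removes almost no one. If a later visit is meant, it removes subjects who stop, die or are lost before Day 7.

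**Step 3. Effect of one excluded subject.** Input from the protocol: n = 62 per arm. Assumptions: all 62 are dosed, one falls outside mITT, and x of the 62 have an SAE.

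- Rate on all dosed subjects: x/62.
- Rate on mITT if the excluded subject had an SAE: (x − 1)/61.
- Rate on mITT if the excluded subject had none: x/61.

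| x (assumed) | All dosed | mITT, excluded subject had an SAE | mITT, excluded subject had none |
|---|---|---|---|
| 1 | 1/62 = 1.6% | 0/61 = 0% | 1/61 = 1.6% |
| 2 | 2/62 = 3.2% | 1/61 = 1.6% | 2/61 = 3.3% |
| 4 | 4/62 = 6.5% | 3/61 = 4.9% | 4/61 = 6.6% |

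Over this range, one exclusion lowers the arm's rate by 1.5 to 1.6 percentage points or raises it by at most 0.1. With two excluded subjects who both had an SAE, and one other SAE in the arm, 3/62 = 4.8% becomes 1/60 = 1.7%.

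**Step 4. Chance that an event is lost.** If k dosed subjects are excluded and each has event risk p, independently, the chance of losing at least one subject with an event is 1 − (1 − p)^k. Both k and p are assumptions.

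- k = 1, p = 5%: 1 − 0.95 = 5%.
- k = 3, p = 10%: 1 − 0.90³ = 27%.
- k = 6, p = 20%: 1 − 0.80⁶ = 74%.

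The last case is the upper end of the assumed range, not a forecast.

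**The case against.** The strongest reply is that the safety sentence already states the usual rule, at least one dose, and that the mention of mITT is a loose label for the same people. The separate use of a Safety population in SAP section 5.1 fits that reading. This is a fair account of what the authors may have intended. It does not settle the text, because the Methods of Analysis line names mITT again and adds the word only, and section 5.1 refers back to the same conflicting definition.

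The second reply is that hardly anyone can be affected. The screening note bars known ineligible patients, complete misallocation of product is improbable, and the visit condition is close to empty if Day 1 counts. This stands as a limit on size. What remains is mainly breaches found after dosing, for which the documents give no number.

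A reader might also infer that subjects withdrawn because of an adverse event disappear from the safety tables. The documents do not support that: withdrawal is not an mITT criterion, so an eligible subject who took the assigned product and completed a visit stays in.

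**Conclusion.** The definitions conflict, and the operative instruction selects the narrower set. I hold that with high confidence, since it rests only on the SAP's wording. The SAP should be corrected, but the expected effect is small. In the single-exclusion illustration it is at most about 1.6 percentage points in one arm, with 62 dosed and assumed event counts. The direction is unknown: the rate falls if the excluded subject had an event and rises very slightly if not, and either arm could be affected.

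Two stronger conclusions would go too far. One is that the rule favours ViraCide or is meant to hide events. The mITT conditions are worded alike for both arms, and nothing in the documents indicates which arm would lose subjects. The other is that analysis-set wording also conceals deaths, because the PP definition mentions completing all visits. That depends on reading the PP clause as restrictive, which its wording does not force, and survival is also planned on mITT, where deaths in eligible dosed subjects with a completed visit are counted. This point gives no basis for changing the efficacy sets.

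**What to change.** Make three wording changes in SAP section 3:

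1. Define the safety set as *all subjects who received at least one dose, analysed by product received*, with no eligibility or visit condition.
2. Delete the closing words of the safety definition that equate it with mITT.
3. Replace "And Safety variables as per mITT only" with *Safety variables will be analysed on the safety set.*

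The third change covers the AE and SAE summaries, the chi-square comparison, and the vital-sign and laboratory analyses in section 5.4. The PP and mITT definitions for efficacy can stay as they are for this purpose.

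The cost is a few sentences, with no change to data collection, design or sample size. The safety and mITT denominators may then differ slightly, and a few ineligible subjects may enter the safety tables. A line in the participant disposition table giving the number dosed but outside mITT, by arm, would explain any difference.
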